12.2.3.2 Rifampicin

Rifampicin concentrations will be summarized by study day using appropriate descriptive statistics.

12.2.3.3 4β-hydroxycholesterol and cholesterol

Results for 4β-hydroxycholesterol and cholesterol along with the ratio of post-treatment to pre-treatment concentration will be listed for individual volunteers and summarised by analyte and study day. Descriptive statistics (n, mean, SD, CV, minimum, median and maximum) will include the ratio of post-treatment to pre-treatment concentrations. These ratios with 90% CIs calculated on log-transformed data may also be determined with results back-transformed for presentation.

12.2.4 Interim analyses

Not applicable.

12.3 Determination of sample size

The primary objective of this study is to investigate the effect of multiple 600 mg (2 x 300 mg) oral doses of rifampicin on the exposure of a single 75 mg oral dose of selumetinib in healthy volunteers by comparing AUC and C_{max} of selumetinib in the presence and absence of rifampicin.

A sample size of 20 evaluable healthy volunteers has been selected based on the desire to gain adequate information while exposing as few healthy volunteers as possible to study procedures. Twenty-four healthy volunteers will be enrolled into the study in order to have at least 20 evaluable healthy volunteers complete the study (allowing for an approximate 20% dropout rate).

Table 6 displays expected 90% CI for a range of possible drug-drug interaction effects at the selected sample size of 20 evaluable volunteers. Within-volunteer estimates of coefficient of variation (CV) (16.9% for AUC and 34.0% for C_{max}) observed in a prior clinical study (Study D1532C00066) were used in these calculations. These 90% CIs demonstrate that good precision of the drug-drug interaction effect will be achieved from a sample size of 20 evaluable healthy volunteers.

Table 6 90% Confidence intervals for C_{max} and AUC varying drug-drug interaction effects given an evaluable sample size of 20

Parameter	Drug-drug interaction effect: Relative reduction of C_{max} or AUC (geometric least squares means ratio)						
	70% (0.3)	60% (0.4)	50% (0.5)	40% (0.6)	30% (0.7)	20% (0.8)	10% (0.9)
C_{max}	0.25, 0.36	0.34, 0.48	0.42, 0.59	0.51, 0.71	0.59, 0.83	0.67, 0.95	0.76, 1.07
AUC	0.27, 0.33	0.37, 0.44	0.46, 0.55	0.55, 0.65	0.64, 0.76	0.73, 0.87	0.82, 0.98

C_{max} : maximum concentration in the sampled matrix

AUC: area under the concentration-time curve in the sampled matrix from time zero to infinity

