Following log-transformation of selumetinib C_{\max} , AUC and AUC_{0-t} will be separately analyzed by mixed effect analysis of variance, fitting a fixed effect term for treatment (selumetinib + rifampicin vs selumetinib alone) and random effects for volunteer. Point estimates and adjusted 90% confidence interval (CI) for the difference in treatment (selumetinib + rifampicin or selumetinib alone) will be constructed. The point estimate and adjusted 90% CIs will then be exponentially back transformed to provide point and CI estimates for the ratio of interest (ie, C_{\max} or AUC of selumetinib contrasting with or without co-administration with rifampicin).

Analyses will be conducted for selumetinib and separately for the metabolite N-desmethyl selumetinib. However, note that sample size was determined according to the precision of the drug-drug interactions effect on selumetinib, rather than the metabolite.

Although descriptive CIs will be presented for some outcomes, this study has not been powered to perform any formal hypothesis testing.

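### Table 6 computes its 90% intervals for 20 volunteers with the normal quantile rather than t on 19 degrees of freedom, so half of the printed limits are too narrow by 0.01

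*Protocol*

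**What the plan says.** Protocol section 12.3 sets the evaluable sample at 20, with 24 enrolled to allow for dropout. It takes within-volunteer CVs of 16.9% for AUC and 34.0% for Cmax from an earlier study of selumetinib in healthy volunteers. It then states: "Table 6 displays expected 90% CI for a range of possible drug-drug interaction effects at the selected sample size of 20 evaluable volunteers". For true ratios 0.3, 0.4, ... 0.9, the Cmax row reads "0.25, 0.36 0.34, 0.48 0.42, 0.59 0.51, 0.71 0.59, 0.83 0.67, 0.95 0.76, 1.07" and the AUC row reads "0.27, 0.33 0.37, 0.44 0.46, 0.55 0.55, 0.65 0.64, 0.76 0.73, 0.87 0.82, 0.98". The section concludes from these intervals that 20 evaluable volunteers give good precision. It does not name the multiplier or formula, and does not call the table an approximation.

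Section 12.2.3.1 specifies the analysis of the log-transformed parameters as a mixed-effect analysis of variance, "fitting a fixed effect term for treatment (selumetinib + rifampicin vs selumetinib alone) and random effects for volunteer". The same section says that the study is not powered for formal hypothesis testing.

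**The concern.** Each evaluable volunteer contributes one value on selumetinib alone and one on selumetinib with rifampicin. With treatment fixed and volunteer random, and every pair complete, the treatment contrast is a paired comparison. Its variance is estimated from the data on n - 1 degrees of freedom, so a 90% interval at 20 volunteers uses t(0.95, 19). A table built on the normal quantile treats the variance as known and shows intervals narrower than this analysis would give at the same observed CV.

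At stake is the accuracy of the table behind the precision claim. The result of the trial is not at stake, because the reported intervals will come from the model and not from Table 6.

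**Working it through.** **Inputs.** From section 12.3: n = 20; CV = 0.340 (Cmax) and 0.169 (AUC); 90% two-sided level; true ratios 0.3 to 0.9. From section 12.2.3.1: log scale, treatment fixed, volunteer random.

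**Formula.** s = sqrt(ln(1 + CV²)); SE = s × sqrt(2/n); limits = ratio × exp(± q × SE), where q is the multiplier.

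- Cmax: s = sqrt(ln(1 + 0.340²)) = 0.3307; SE = 0.3307 × sqrt(2/20) = 0.1046.
- AUC: s = sqrt(ln(1 + 0.169²)) = 0.1678; SE = 0.1678 × sqrt(2/20) = 0.0531.

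**Step 1: reproduce Table 6.** With q = 1.645 the log half-widths are 0.1720 (Cmax) and 0.0873 (AUC), that is, factors of 1.188 and 1.091. All 28 limits match the print to two decimals. For example, Cmax at 0.9 gives 0.758 to 1.069 (printed 0.76, 1.07), and AUC at 0.9 gives 0.825 to 0.982 (printed 0.82, 0.98).

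Working backwards, the printed limits allow q only between 1.643 and 1.648 for Cmax and between 1.640 and 1.653 for AUC. The t value of 1.729 lies outside both ranges, so rounding does not explain the difference. Other t degrees of freedom (18, 23, 38, 57), s set equal to the CV, SE = s/sqrt(n), and n = 24 were also tried. None reproduces all the limits.

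**Step 2: use the multiplier of the planned analysis.** With q = t(0.95, 19) = 1.729 the log half-widths become 0.1809 and 0.0918 (factors 1.198 and 1.096). The ratio to Table 6 is 1.729/1.645 = 1.051 for both parameters.

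| True ratio | Cmax printed | Cmax with t(19) | AUC printed | AUC with t(19) |
|---|---|---|---|---|
| 0.3 | 0.25, 0.36 | 0.25, 0.36 | 0.27, 0.33 | 0.27, 0.33 |
| 0.4 | 0.34, 0.48 | **0.33**, 0.48 | 0.37, 0.44 | **0.36**, 0.44 |
| 0.5 | 0.42, 0.59 | 0.42, **0.60** | 0.46, 0.55 | 0.46, 0.55 |
| 0.6 | 0.51, 0.71 | **0.50**, **0.72** | 0.55, 0.65 | 0.55, **0.66** |
| 0.7 | 0.59, 0.83 | **0.58**, **0.84** | 0.64, 0.76 | 0.64, **0.77** |
| 0.8 | 0.67, 0.95 | 0.67, **0.96** | 0.73, 0.87 | 0.73, **0.88** |
| 0.9 | 0.76, 1.07 | **0.75**, **1.08** | 0.82, 0.98 | 0.82, **0.99** |

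Changed limits are in bold: 9 of 14 for Cmax and 5 of 14 for AUC, 14 of 28 in all. Each differs by 0.01 and each widens the interval. No interval changes its relation to 1.

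**Step 3: average over the sampling of the standard deviation.** The 5.1% holds when the observed standard deviation equals the planning value. On 19 degrees of freedom the sample standard deviation averages 0.987 of the true one, so the mean log width exceeds Table 6 by a factor of 1.051 × 0.987 = 1.037, about 3.7%. The probability that a realised interval is wider than printed is P(χ²₁₉/19 > (1.645/1.729)²) = 0.58. About 42% would be narrower.

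**Step 4: other numbers of completers, at the planning CV.** Table 6 corresponds to 1.645 × sqrt(2/20) = 0.520 times s. The t interval gives 0.532 with 21 completers and 0.519 with 22.

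**The case against.** The strongest objection is that nothing depends on the second decimal. The protocol sets no equivalence bound and no target width, and it disclaims formal testing. Unrounded, the largest shift is 0.0095 for Cmax and 0.0044 for AUC. Twenty is also a minimum: with 24 enrolled, 22 completers would already give the printed half-widths at the planning CV. All of this stands and makes the point minor. It does not make the table right, because the table is labelled as the 90% interval "at the selected sample size of 20 evaluable volunteers" and carries no note that it is approximate.

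A reader might infer three stronger things that the documents do not support.

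- **That the sample size rests on Table 6 alone.** Sections 3.2 and 12.3 both say that 20 was chosen to gain adequate information while exposing few volunteers, and section 3.2 points to section 12.3 for the implications. The table describes the precision of a number chosen on those grounds; the number was not solved from the table.
- **That the trial's actual intervals are bound to be wider than printed.** The realised width depends on the observed standard deviation and on the number who complete. Even at the planning CVs with exactly 20 pairs, about 42% of realised intervals would be narrower.
- **That the reported intervals will fall short of 90% coverage.** A 1.645 multiplier on 19 degrees of freedom would cover 88.4%, but nothing in section 12.2.3.1 says that a normal multiplier will be used in the analysis.

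**Conclusion.** The point holds as a small numerical error in a planning table. Table 6 uses 1.645 where the planned analysis, with 20 complete pairs, implies 1.729. It therefore understates the log-scale width by 5.1% at the planning CVs, or by about 3.7% on average, and prints 14 of 28 limits too narrow by 0.01.

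The result assumes exactly 20 complete pairs (hence 19 degrees of freedom) and the CVs stated in section 12.3. The choice of 20 evaluable volunteers, the enrolment of 24, the statement that precision is good and the final analysis are unaffected.

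**What to change.** Replace the entries of Table 6 with the t(19) values and print the formula beneath it: ratio × exp(± t(0.95, 19) × s × sqrt(2/20)), with s = sqrt(ln(1 + CV²)).

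- Cmax, ratios 0.3 to 0.9: 0.25-0.36, 0.33-0.48, 0.42-0.60, 0.50-0.72, 0.58-0.84, 0.67-0.96, 0.75-1.08.
- AUC, ratios 0.3 to 0.9: 0.27-0.33, 0.36-0.44, 0.46-0.55, 0.55-0.66, 0.64-0.77, 0.73-0.88, 0.82-0.99.

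The cost is one replaced table and one line of text. The stated precision becomes slightly less favourable; no data, procedures or volunteers are added.

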13.2 Overdose

For the purposes of this study, exceeding the dosage requirements specified in this clinical study protocol represents an overdose. There is no known antidote for selumetinib. In case of suspected overdose, the healthy volunteer should be treated according to standard medical practice based on the investigator's judgment. Cases of overdose will be recorded as follows:

- An overdose with associated AEs is recorded as the AE diagnosis/symptoms on the relevant AE modules in the eCRF and on the Overdose eCRF module.
- An overdose without associated symptoms is only reported on the Overdose eCRF module.

If an overdose on an AstraZeneca investigational product occurs in the course of the study, then investigators or other study center personnel will inform appropriate AstraZeneca representatives immediately, or **no later than 24 hours** of when he or she becomes aware of it.

The designated AstraZeneca representative will work with the investigator to ensure that all relevant information is provided to the AstraZeneca Patient Safety data entry site.

For overdoses associated with an SAE, standard reporting timelines apply, see Section 6.3.4. For other overdoses, reporting should be done within 30 days.

13.3 Pregnancy

All outcomes of pregnancies in female volunteers or pregnancies in partners of healthy male volunteers should be reported to AstraZeneca.

13.3.1 Maternal exposure

Women of childbearing potential are not allowed to be included in this study. Should a pregnancy still occur, the investigational product should be discontinued immediately and the pregnancy reported to AstraZeneca.

Pregnancy itself is not regarded as an AE unless there is a suspicion that the investigational product under study may have interfered with the effectiveness of a contraceptive medication. Congenital abnormalities/birth defects and spontaneous miscarriages should be reported and handled as SAEs. Elective abortions without complications should not be handled as AEs. The outcome of all pregnancies (spontaneous miscarriage, elective termination, ectopic pregnancy, normal birth or congenital abnormality) should be followed up and documented even if the subject was discontinued from the study.

If any pregnancy occurs in the course of the study, then investigators or other study center personnel will inform appropriate AstraZeneca representatives immediately, or **no later than 24 hours** of when he or she becomes aware of it.

The designated AstraZeneca representative works with the principal investigator to ensure that all relevant information is provided to the AstraZeneca Patient Safety data entry site within 1 or 5 days for SAEs, see Section 6.3.4 and within 30 days for all other pregnancies.

The same timelines apply when outcome information is available.

The PREGREP module in the pCRF is used to report the pregnancy and the PREGOUT is used to report the outcome of the pregnancy.

13.3.2 Paternal exposure

Healthy volunteers should refrain from fathering a child or donating sperm during the study and for 12 weeks after the last investigational product administration.

Pregnancy of the healthy volunteer's partners is not considered to be an AE. However, the outcome of all pregnancies (spontaneous miscarriage, elective termination, ectopic pregnancy, normal birth or congenital abnormality) should if possible be followed up and documented.

The outcome of any conception occurring from the date of the first administration until 30 days after the last investigational product administration should be followed up and documented.

14. LIST OF REFERENCES (Not applicable)

Clinical Study Protocol Appendix A

Drug Substance	Selumetinib
Study Code	D1532C00085
Edition Number	1

Appendix B
Additional Safety Information

FURTHER GUIDANCE ON THE DEFINITION OF A SERIOUS ADVERSE EVENT (SAE)

Life threatening

‘Life-threatening’ means that the subject was at immediate risk of death from the AE as it occurred or it is suspected that use or continued use of the product would result in the subject’s death. ‘Life-threatening’ does not mean that had an AE occurred in a more severe form it might have caused death (eg, hepatitis that resolved without hepatic failure).

Hospitalisation

Outpatient treatment in an emergency room is not in itself a serious AE, although the reasons for it may be (eg, bronchospasm, laryngeal oedema). Hospital admissions and/or surgical operations planned before or during a study are not considered AEs if the illness or disease existed before the subject was enrolled in the study, provided that it did not deteriorate in an unexpected way during the study.

Important medical event or medical intervention

Medical and scientific judgement should be exercised in deciding whether a case is serious in situations where important medical events may not be immediately life threatening or result in death, hospitalisation, disability or incapacity but may jeopardize the subject or may require medical intervention to prevent one or more outcomes listed in the definition of serious. These should usually be considered as serious.

Simply stopping the suspect drug does not mean that it is an important medical event; medical judgement must be used.

Examples of such events are:

- Angioedema not severe enough to require intubation but requiring iv hydrocortisone treatment
- Hepatotoxicity caused by paracetamol (acetaminophen) overdose requiring treatment with N-acetylcysteine
- Intensive treatment in an emergency room or at home for allergic bronchospasm
- Blood dyscrasias (eg, neutropenia or anaemia requiring blood transfusion, etc) or convulsions that do not result in hospitalisation
- Development of drug dependency or drug abuse.

A GUIDE TO INTERPRETING THE CAUSALITY QUESTION

The following factors should be considered when deciding if there is a “reasonable possibility” that an AE may have been caused by the drug.

- Time Course. Exposure to suspect drug. Has the subject actually received the suspect drug? Did the AE occur in a reasonable temporal relationship to the administration of the suspect drug?
- Consistency with known drug profile. Was the AE consistent with the previous knowledge of the suspect drug (pharmacology and toxicology) or drugs of the same pharmacological class? OR could the AE be anticipated from its pharmacological properties?
- Dechallenge experience. Did the AE resolve or improve on stopping or reducing the dose of the suspect drug?
- No alternative cause. The AE cannot be reasonably explained by another aetiology such as the underlying disease, other drugs, other host or environmental factors.
- Rechallenge experience. Did the AE reoccur if the suspected drug was reintroduced after having been stopped? AstraZeneca would not normally recommend or support a rechallenge.
- Laboratory tests. A specific laboratory investigation (if performed) has confirmed the relationship?

A “reasonable possibility” could be considered to exist for an AE where one or more of these factors exist.

In contrast, there would not be a “reasonable possibility” of causality if none of the above criteria apply or where there is evidence of exposure and a reasonable time course but any dechallenge (if performed) is negative or ambiguous or there is another more likely cause of the AE.

In difficult cases, other factors could be considered such as:

- Is this a recognised feature of overdose of the drug?
- Is there a known mechanism?

Ambiguous cases should be considered as being a “reasonable possibility” of a causal relationship unless further evidence becomes available to refute this. Causal relationship in cases where the disease under study has deteriorated due to lack of effect should be classified as no reasonable possibility.

Clinical Study Protocol Appendix C

Drug Substance	Selumetinib
Study Code	D1532C00085
Edition Number	1

**Appendix C
International Airline Transportation Association (IATA) 6.2
Guidance Document**

LABELLING AND SHIPMENT OF BIOHAZARD SAMPLES

International Airline Transportation Association (IATA) classifies biohazardous agents into 3 categories (http://www.iata.org/whatwedo/cargo/dangerous_goods/infectious_substances.htm). For transport purposes the classification of infectious substances according to risk groups was removed from the Dangerous Goods Regulations (DGR) in the 46th edition (2005). Infectious substances are now classified either as Category A, Category B or Exempt. There is no direct relationship between Risk Groups and categories A and B.

Category A Infectious Substances are infectious substances in a form that, when exposure to it occurs, is capable of causing permanent disability, life-threatening or fatal disease in otherwise healthy humans or animals. Category A pathogens are eg, Ebola, Lassa fever virus:

- are to be packed and shipped in accordance with IATA Instruction 602.

Category B Infectious Substances are infectious Substances that do not meet the criteria for inclusion in Category A. Category B pathogens are eg, Hepatitis A, B, C, D, and E viruses, Human immunodeficiency virus (HIV) types 1 and 2. They are assigned the following UN number and proper shipping name:

- UN 3373 – Biological Substance, Category B
- are to be packed in accordance with UN3373 and IATA 650

Exempt - all other materials with minimal risk of containing pathogens

- Clinical trial samples will fall into Category B or exempt under IATA regulations
- Clinical trial samples will routinely be packed and transported at ambient temperature in IATA 650 compliant packaging (http://www.iata.org/whatwedo/cargo/dangerous_goods/infectious_substances.htm)
- **Biological samples transported in dry ice require additional dangerous goods specification for the dry-ice content**
- IATA compliant courier and packaging materials should be used for packing and transportation and packing should be done by an IATA certified person, as applicable

- Samples routinely transported by road or rail are subject to local regulations which require that they are also packed and transported in a safe and appropriate way to contain any risk of infection or contamination by using approved couriers and packaging / containment materials at all times. The IATA 650 biological sample containment standards are encouraged wherever possible when road or rail transport is used.

Clinical Study Protocol Appendix D

Drug Substance	Selumetinib
Study Code	D1532C00085
Edition Number	1

1. INTRODUCTION

During the course of the study the Investigator will remain vigilant for increases in liver biochemistry. The investigator is responsible for determining whether a patient meets potential Hy's Law (PHL) criteria at any point during the study.

The Investigator participates, together with AstraZeneca clinical project representatives, in review and assessment of cases meeting PHL criteria to agree whether Hy's Law (HL) criteria are met. HL criteria are met if there is no alternative explanation for the elevations in liver biochemistry other than Drug Induced Liver Injury (DILI) caused by the Investigational Medicinal Product (IMP).

The Investigator is responsible for recording data pertaining to PHL/HL cases and for reporting Adverse Events (AE) and Serious Adverse Events (SAE) according to the outcome of the review and assessment in line with standard safety reporting processes.

2. DEFINITIONS

Potential Hy's Law (PHL)

Aspartate aminotransferase (AST) or alanine aminotransferase (ALT) ≥ 3 x upper limit of normal (ULN) at any point during the study irrespective of an increase in alkaline phosphatase (ALP). The elevations do not have to occur at the same time or within a specified time frame.

Hy's Law (HL)

AST or ALT ≥ 3 x ULN, where no other reason, other than the IMP, can be found to explain the combination of increases, eg, elevated ALP indicating cholestasis, viral hepatitis, another drug. The elevations do not have to occur at the same time or within a specified time frame.

3. IDENTIFICATION OF POTENTIAL HY'S LAW CASES

In order to identify cases of PHL it is important to perform a comprehensive review of laboratory data for any patient who meets any of the following identification criteria in isolation or in combination:

- ALT ≥ 3 xULN
- AST ≥ 3 xULN
- TBL ≥ 2 xULN

When a patient meets any of the identification criteria, in isolation or in combination, the central laboratory will immediately send an alert to the Investigator (also sent to AstraZeneca representative).

The Investigator will also remain vigilant for any local laboratory reports where the identification criteria are met, where this is the case the Investigator will:

- Request a repeat of the test (new blood draw) by the central laboratory
- Complete the appropriate unscheduled laboratory CRF module(s) with the original local laboratory test result

When the identification criteria are met from central or local laboratory results the Investigator will without delay:

- Determine whether the patient meets PHL criteria (see Section 2 of this Appendix for definition) by reviewing laboratory reports from all previous visits (including both central and local laboratory results)

The Investigator will without delay review each new laboratory report and if the identification criteria are met will:

- Notify the AstraZeneca representative
- Determine whether the patient meets PHL criteria (see Section 2 of this Appendix for definition) by reviewing laboratory reports from all previous visits
- Promptly enter the laboratory data into the laboratory CRF

